8.3 Study procedures

See flowchart under "study design (page 15)."

8.4 Withdrawal of individual subjects

Subjects can leave the study at any time for any reason if they wish to do so without any consequences. The investigator can decide to withdraw a subject from the study for urgent medical reasons.

8.4.1 Specific criteria for withdrawal (if applicable)

In case of unexpected events requiring opioids or anaesthetics outside the protocol during the procedure, the patient will be withdrawn from the study.

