objective of this trial. Secondary objectives of this trial are the time until discharge criteria from the recovery room are met, the incidence of postoperative delirium, the difference in intra-operative blood pressure between the intervention group and the control group, the incidence of recall of intraoperative events, adverse events and DoH during GA (as measured by the Narcotrend monitorTM).

Nature and extent of the burden and risks associated with participation, benefit and group relatedness:

In patients randomised to the intervention group, the anaesthetic agent sevoflurane will be administered on the basis of objective measures of anaesthetic depth, the typical DSA pattern for GA. We expect a significantly faster speed of emergence and recovery based on clinical experiences with the use of DSA. The NarcotrendTM monitor is validated for use in paediatric patients. There are thus no additional risk factors apart from those, which are inherent with general anaesthesia. Patient randomised to the control group will receive standard treatment, that is delivery of sevoflurane based on a MAC of 0.9 respectively an end tidal sevoflurane concentration of 2.3%.

A non-invasive therapeutical intervention (DSA based conduct of GA) should result in the advantage of faster recovery, without any additional risk factor.

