4.2 Inclusion criteria

In order to be eligible to participate in this study, a subject must meet all of the following criteria:

- Written informed consent of the parents/legal representatives
- Age > 6 months and < 12 years
- Surgical procedure requiring GA supplemented with caudal analgesia
- Ability of the parents or legal guardians to communicate in Dutch

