5. TREATMENT OF SUBJECTS

The effect of DSA on recovery of anaesthesia in children protocol

Standard anaesthesia monitoring is used during the procedure, ECG, pulse-oxymetry, capnometry and non-invasive measurement of blood-pressure.

Patients randomized to the control group are also attached to the Narcotrend monitor, but with the screen of the monitor obscured. The electroencephalographic data will later be compared to the data of the intervention group in order to assess for differences of depth of hypnosis during the procedure.

After complete recovery from GA, the day thereafter and two weeks later, parents or legal guardians will be contacted via telephone for a systematic interview with the patient if aged > 6 years. This systematic interview is the “Modified Brice-interview”, which is the golden standard for the detection of recall of intraoperative events.^{17,18} Brice interviews will only be performed in patients of at least 6 years of age, because it is known that interviews taken in children of younger ages are likely not to provide the interviewer with reliable information. At the end of the procedure, sevoflurane will be stopped and washed out with 10L flow, FiO₂ 0.5. The patients will be otherwise left undisturbed on the operation table. The sound level in the operation theatre will be reduced to a minimum.

The speed of emergence and recovery will be assessed with the Steward Recovery Score from Anaesthesia.¹³

The incidence of postoperative delirium will be assessed with the Cornell Assessment of Postoperative Delirium (CAPD).^{14,15}

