8.6 Follow-up of subjects withdrawn from treatment

Not applicable

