10.3 Other study parameters

Descriptive statistics will be applied to demographic variables, continuous variables such as discharge times, incidence of recall of events during the procedure (awareness) and adverse events. All datasets will be tested for normality by means of the Shapiro-Wilk normality test.

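### Children given an opioid or anaesthetic outside the protocol drop out of the recall and harm summaries by rule, and recall is collected in too few children to confirm that DSA guidance adds no awareness risk

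*Combined protocol and SAP*

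**What the plan says.** Three sections of the combined protocol and SAP act together.

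- Section 8.4.1: "In case of unexpected events requiring opioids or anaesthetics outside the protocol during the procedure, the patient will be withdrawn from the study".
- Section 5.3 classes any opioid or anaesthetic used outside the protocol as escape medication and excludes the child from analysis. It does not limit this to the efficacy analysis.
- Section 8.6, headed "Follow-up of subjects withdrawn from treatment", is marked not applicable.

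Recall and adverse events are secondary endpoints (sections 2 and 8.1.2). Section 10.3 plans descriptive statistics for "incidence of recall of events during the procedure (awareness) and adverse events" and gives no denominator and no rule for withdrawn children. Escape medication is not among the endpoints.

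Section 5 describes the modified Brice interview at three times: after complete recovery, the next day and two weeks later. It limits the interview by age: "Brice interviews will only be performed in patients of at least 6 years of age", because "interviews taken in children of younger ages are likely not to provide the interviewer with reliable information". The same paragraph also gives the limit as "systematic interview with the patient if aged > 6 years". Eligibility in section 4.2 is "Age > 6 months and < 12 years".

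Section 8.2 says that the person giving the anaesthetic cannot be blinded. The Summary describes the expected benefit as coming "without any additional risk factor".

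**The concern.** The intervention changes how sevoflurane is titrated, so its foreseeable harm is anaesthesia that is too light. Section 10.2 itself defines a category for that state. An unplanned anaesthetic or opioid during surgery is a plausible, though not specific, marker of it. Under the written rules, that event takes the child out of the summaries meant to show harm, and it is not reported as a result in its own right.

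The event occurs after randomisation. In practice the choice to give the drug lies with someone who knows the allocation, since the blinded assessor is out of theatre until sevoflurane is stopped. The exclusions can therefore differ between arms in number and in kind. Recall is already sought in only part of the sample, so a small count could rest on a subset that is both small and selected. Once the interview dates have passed, the missing interviews cannot be recovered.

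**Working it through.** **Which rules reach a withdrawn child**

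| Item | What the plan provides after an opioid or anaesthetic outside the protocol |
|---|---|
| Recording of adverse events | Kept: 9.2.1 and 9.2.2 make no exception |
| Following an adverse event to resolution | Kept: 9.4 makes no exception |
| Brice interview | No text keeps it; 8.6 is marked not applicable |
| Place in the recall and adverse-event summaries | Removed by 5.3 |
| The unplanned drug as an outcome | Not listed in 8.1.2 or 10.3 |

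**Inputs.** The plan states no figure for recall. Arm size comes from section 4.4: 51 × 1.10 = 56.1, taken as 56 per arm. How the 51 was reached does not bear on this point. The share of children aged 6 or over is not given, so it is assumed to be 20%, 30% or 52%. The last value spreads ages evenly over 0.5 to 12 years: 6 / 11.5 = 52%.

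**Precision with zero recalls.** The exact (Clopper-Pearson) two-sided 95% upper limit is 1 − 0.025^(1/n). For n = 11 this is 1 − 0.715 = 28.5%. The last column is the chance of at least one recall in an arm, 1 − 0.99^n, at a purely illustrative true rate of 1%, with n as in the second column.

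| Share aged 6 or over | n per arm, all kept | Upper limit | n per arm, 10% lost | Upper limit | Chance of ≥1 recall |
|---|---|---|---|---|---|
| 20% | 56 × 0.20 = 11 | 28.5% | 10 | 30.8% | 10.5% |
| 30% | 56 × 0.30 = 17 | 19.5% | 15 | 21.8% | 15.7% |
| 52% | 56 × 0.52 = 29 | 11.9% | 26 | 13.2% | 25.3% |

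If all 56 in an arm could be interviewed, zero recalls would still leave an upper limit of 6.4%.

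**How many children the rule may remove.** Section 8.5 puts usual dropout near 5%, mostly from equipment failure, and allows 10%. At 5%, 56 × 0.05 = 2.8 children per arm. Of these, 2.8 × 0.20 to 2.8 × 0.52, or 0.6 to 1.5, would be aged 6 or over, for all causes together.

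**What a small loss can hide.** Suppose an arm has 17 children of interview age and 2 are withdrawn without interview. A report of 0/15 is then compatible with anything from 0/17 to 2/17 (11.8%, exact 95% CI 1.5% to 36.4%). A single recall is 1/11 = 9.1% or 1/29 = 3.4% of an arm.

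**The case against.** There is a good case for reading the plan more kindly, and much of it stands.

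- A reader might infer that withdrawn children have no follow-up at all. The documents do not support that: sections 9.2 and 9.4 record, report and follow adverse events without excepting them. An unexpected event in theatre also precedes withdrawal. What is missing is the planned interview and a place in the summaries.
- A reader might infer that the children left out are those most at risk. The documents do not say so. Younger children are omitted because their answers are thought unreliable. Among withdrawn children, an opioid may reflect pain rather than light hypnosis. Adjusting sevoflurane by DSA pattern is the intervention itself and does not trigger withdrawal.
- A reader might infer that the sponsor rests its risk statement on recall data. It does not. The Summary makes the statement in advance, pointing to validation of the monitor, and section 9.5 argues from both arms receiving the same anaesthetics.
- A reader might fear that recall will be divided by all 56 per arm. No section proposes this, although none names the denominator either.
- Light anaesthesia is also measured by DSA category in both arms and at all ages (sections 5 and 10.2). This is a real second measure, but the exclusion in 5.3 applies to it too.
- Many headings are marked not applicable, and the flowchart cited in 8.3 is not available here, so 8.6 may not have been meant to stop safety follow-up. That is possible, but section 5.3 still excludes these children from analysis.

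The numbers affected are probably small, and retaining these children barely narrows the interval. The gain is protection against selection, not precision.

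**Conclusion.** The point holds in a limited form. As written, sections 5.3, 8.4.1 and 8.6 condition the recall and adverse-event summaries on a post-randomisation event that may be linked to inadequate anaesthesia and arises under an unblinded anaesthetist. The direction of any bias between arms cannot be told from the documents. On the plan's usual dropout, about 0.6 to 1.5 children of interview age per arm would be lost for all causes, and fewer for this one if most losses are equipment failures.

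Separately, with 11 to 29 interviewed per arm, zero recalls leaves upper limits of 28.5% to 11.9%. The trial can describe recall but cannot confirm the absence of added awareness risk, even if every eligible child is interviewed. These figures rest on the assumed 20% to 52% share aged 6 or over.

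The age limit is deliberate and reasoned, so it is a limitation to state rather than an error. The change should be made because it is cheap and missed interviews cannot be recovered.

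**What to change.** 1. Reconcile sections 5.3, 8.4.1 and 8.6 so that children withdrawn for an extra opioid or anaesthetic stay in safety follow-up (adverse events, and the Brice interview where age allows) and in the safety summaries, unless consent is withdrawn.
2. In sections 8.1.2 and 10.3, report unplanned opioid or anaesthetic use by arm in all randomised children.
3. In section 10.3, report recall by arm as events over children interviewed, with the numbers eligible and withdrawn and an exact 95% confidence interval. State that the figure does not cover younger children. Reconcile the two wordings of the age limit in section 5.

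The cost is protocol and SAP wording, plus up to three telephone interviews for each of a few children. No treatment rule changes.

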8.5 Replacement of individual subjects after withdrawal

In order to compete with possible dropouts, due to withdrawal for whatever reason or due to protocol violation, the sample size of the study is about 10% in excess of the results of the sample size calculation. In paediatric depth of anaesthesia studies dropout rates are usually within the range of +/- 5% and mostly due to equipment failure. As a consequence of secondary exclusion due to protocol violation or data registration failure, we choose to increase the number of subjects with 10% on beforehand. There is no need to replace individual subject after withdrawal.

8.6 Follow-up of subjects withdrawn from treatment

Not applicable

8.7 Premature termination of the study

Not applicable

9. SAFETY REPORTING

9.1 Temporary halt for reasons of subject safety

In accordance to section 10, subsection 4, of the WMO, the sponsor will suspend the study if there is sufficient ground that continuation of the study will jeopardise subject health or safety. The sponsor will notify the accredited METC without undue delay of a temporary halt including the reason for such an action. The study will be suspended pending a further positive decision by the accredited METC. The investigator will take care that all subjects are kept informed.

9.2 AEs, SAEs and SUSARs

9.2.1 Adverse events (AEs)

Adverse events are defined as any undesirable experience occurring to a subject during the study, whether or not considered related to [the investigational product / trial procedure/ the experimental intervention]. All adverse events reported spontaneously by the subject or observed by the investigator or his staff will be recorded.

9.2.2 Serious adverse events (SAEs)

A serious adverse event is any untoward medical occurrence or effect that

- results in death;
- is life threatening (at the time of the event);
- requires hospitalisation or prolongation of existing inpatients' hospitalisation;
- results in persistent or significant disability or incapacity;
- is a congenital anomaly or birth defect; or
- any other important medical event that did not result in any of the outcomes listed above due to medical or surgical intervention but could have been based upon appropriate judgement by the investigator.

An elective hospital admission will not be considered as a serious adverse event.

The investigator will report all SAEs to the sponsor without undue delay after obtaining knowledge of the events. .

The sponsor will report the SAEs through the web portal *ToetsingOnline* to the accredited METC that approved the protocol, within 7 days of first knowledge for SAEs that result in death or are life threatening followed by a period of maximum of 8 days to complete the initial preliminary report. All other SAEs will be reported within a period of maximum 15 days after the sponsor has first knowledge of the serious adverse events.

9.2.3 Suspected unexpected serious adverse reactions (SUSARs)

Not applicable

9.3 Annual safety report

Not applicable

9.4 Follow-up of adverse events

All AEs will be followed until they have abated, or until a stable situation has been reached. Depending on the event, follow up may require additional tests or medical procedures as indicated, and/or referral to the general physician or a medical specialist. SAEs need to be reported till end of study within the Netherlands, as defined in the protocol

9.5 Data Safety Monitoring Board (DSMB) / Safety Committee

Participants of this study receive general anaesthesia and caudal analgesia for a planned surgical procedure. Both the intervention-group and the control-group receive the same anaesthetics. The only risk in this study is the risk that is inherent with general anaesthesia, which will be applied regardless whether or not the patients agree to participate in the study. General anaesthesia with sevoflurane supplemented with caudal anaesthesia is considered appropriate and safe for many surgical procedures and is frequently used in general practice in the ErasmusMC Sophia children's hospital.

As a result of a risk assessment using the guideline "kwaliteitsborging van mensgebonden onderzoek", provided by the Dutch Federation of University Medical Centres (NFU), we conclude that this study has a negligible risk level.

10. STATISTICAL ANALYSIS

10.1 Primary study parameter(s)

The time interval between the end of anaesthetic drug application and the moment when discharge criteria from the operating room are met (Steward score ≥ 3) is compared between the study groups. Therefore datasets will first be tested for normality by means of the Shapiro-Wilk normality test. As appropriate, either a Mann-Whitney-U-test or a t-test will be performed.

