1.5 Post-anaesthesia discharge criteria – The Steward Post-Anaesthetic Recovery Score

The 'Simplified Post-Anaesthetic Recovery Score', published by Steward¹³, is the golden standard for assessment of recovery from Anaesthesia:

Consciousness	Score
Awake	2
Responds to stimuli	1
Not responding	0
Airway	
Cough on command or cry	2
Maintaining good airway	1
Requires airway assistance	0
Motor	
Moves limbs purposefully	2
Non-purposeful movement	1
Not moving	0

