1.5.1 Discharge criteria from the operating room

The patient is ready to be transferred from the operating room (OR) to the recovery room when the following criteria are met:

- Responding to stimuli (domain Consciousness) **Score ≥ 1**
- Maintaining good airway (domain Airway) **Score ≥ 1**
- Non-purposeful movements (domain Movement) **Score ≥ 1**

That corresponds with a total Steward Score of ≥ 3 .

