1.5.2 Discharge criteria from the recovery room

Complete recovery from general anaesthesia is the prerequisite for discharge from the recovery room. It is achieved when the patient meets the following criteria:

- Awake (domain Consciousness) **Score 2**
- Coughing on command or crying (domain Airway) **Score 2**
- Moving limbs purposefully (domain Movement) **Score 2**

That corresponds with a total Steward Score of 6.

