2. OBJECTIVES

Primary Objective: the influence of density spectral array monitoring with the Narcotrend™ monitor on the speed of emergence from general anaesthesia with sevoflurane. The speed of emergence is defined as the time interval between the end of hypnotic drug application and the moment when discharge criteria from the operating room are met (defined as a Steward score ≥ 3).

Secondary Objectives:

- Total time from discontinuation of anaesthetic drug delivery until discharge from the post anaesthesia care unit.
- The incidence of postoperative delirium by the Cornell Assessment of Postoperative Delirium (CAPD) score.^{14,15}
- The difference in intra-operative blood pressure between the intervention group and the control group.
- Differences of depth of hypnosis during the procedure, as measured by the Narcotrend monitor™.
- Incidence of recall of events during the procedure (awareness)
- Adverse events

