8. METHODS

8.1 Study parameters/endpoints

8.1.1 Main study parameter/endpoint

The primary endpoint of the study is the time interval between the termination of anaesthetic drug delivery and discharge from the operating theatre according to predefined discharge criteria.

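### The primary endpoint's bracketed rule, a total Steward score of at least 3, is not equivalent to the operating-room discharge criteria it stands for (every domain at least 1)

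*Combined protocol and SAP*

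**What the plan says.** Section 1.5 sets out the Steward score as three domains, each scored 0, 1 or 2. An airway score of 0 is labelled "Requires airway assistance".

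Section 1.5.1 gives the rule for leaving the operating room: "The patient is ready to be transferred from the operating room (OR) to the recovery room when the following criteria are met". Three criteria follow, one per domain, each with a threshold of at least 1; the airway criterion reads "Maintaining good airway (domain Airway"). The section then adds "That corresponds with a total Steward Score of" at least 3.

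The primary endpoint is the time from stopping the anaesthetic until those criteria are met, and it is worded in three ways:

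- Section 2 (Objectives) ends the interval at "the moment when discharge criteria from the operating room are met (defined as a Steward score ≥ 3").
- Section 10.1 (analysis) ends it when "discharge criteria from the operating room are met (Steward score ≥ 3) is compared between the study groups".
- Section 8.1.1 refers to "discharge from the operating theatre according to predefined discharge criteria" and gives no score. The Summary likewise refers to the transfer criteria without a score.

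For the recovery room, section 1.5.2 requires 2 in every domain and says "That corresponds with a total Steward Score of 6".

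**The concern.** Section 1.5.1 contains two rules, a minimum in each domain and a minimum total, and presents them as the same thing. Sections 2 and 10.1 carry forward only the total. A total lets a high score in one domain make up for a zero in another; a minimum in each domain does not.

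The primary outcome is a single time-stamp, the first moment at which the rule is met. If the rules differ, two people working from different sections could record different times for the same child. Read literally, the definition in section 2 could also end the interval while the child still fails a listed discharge criterion, including the airway one.

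**Working it through.** **Inputs.** Three domains, each scored 0, 1 or 2 (section 1.5). Rule A: every domain at least 1 (the list in 1.5.1). Rule B: total at least 3 (1.5.1, 2 and 10.1). Patterns are written (Consciousness, Airway, Movement).

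**The plan's own figures.** The smallest total under rule A is 1 + 1 + 1 = 3, which is where the threshold of 3 comes from. For the recovery room, 2 + 2 + 2 = 6. Because 6 is the maximum, no other pattern reaches it, so the total in 1.5.2 is exactly equivalent to its list.

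**Does A imply B?** Yes. Three scores of at least 1 sum to at least 3.

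**Does B imply A?** There are 3 × 3 × 3 = 27 patterns, and 2 × 2 × 2 = 8 of them meet rule A. By total:

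| Total | Patterns | Every domain at least 1 | At least one domain at 0 |
|---|---|---|---|
| 0 | 1 | 0 | 1 |
| 1 | 3 | 0 | 3 |
| 2 | 6 | 0 | 6 |
| 3 | 7 | 1 | 6 |
| 4 | 6 | 3 | 3 |
| 5 | 3 | 3 | 0 |
| 6 | 1 | 1 | 0 |

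- Rule B is met by 7 + 6 + 3 + 1 = 17 patterns.
- Rule A is met by 1 + 3 + 3 + 1 = 8 patterns, all of which also meet rule B.
- Rule B without rule A: 17 − 8 = 9 patterns.
- Rule A without rule B: 0 patterns.

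The nine discordant patterns are:

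- Consciousness 0: (0,1,2), (0,2,1), (0,2,2)
- Airway 0: (1,0,2), (2,0,1), (2,0,2)
- Movement 0: (1,2,0), (2,1,0), (2,2,0)

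The mismatch lies only at totals of 3 (6 of 7 patterns) and 4 (3 of 6). At a total of exactly 3, the only pattern that meets the listed criteria is (1,1,1).

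**Effect on the time-stamp.** Whenever rule A holds, rule B also holds. The first time B is met therefore cannot be later than the first time A is met, and can be earlier.

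**The case against.** The strongest reply is that the bracket is shorthand. Sections 2 and 10.1 both name the operating-room discharge criteria as the event, and that phrase is the heading of 1.5.1, where the domain thresholds are listed. Section 8.1.1 and the Summary give no total. In 1.5.1 itself, the sentence about the total can be read as a consequence of the list (1 + 1 + 1 = 3), which is true. An assessor who looks up the criteria would find the domain rule. This stands as evidence of intent and keeps the severity low. It does not remove the inconsistency: section 2 uses the language of definition, 1.5.1 carries both rules, and nothing in the documents says that a total of 3 counts only when no domain is 0.

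A second reply is that the pattern counts overstate the practical mismatch. The three Consciousness-0 patterns pair an unresponsive child with coughing on command or crying, with purposeful movement, or with both, and are hard to picture clinically. That is fair. The counts show that the rules differ logically, not how often they would differ in children. Movement-0 patterns are easier to imagine after a caudal block, but that is an assumption.

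Third, the same rule applies in both arms, the assessor is to be blinded (section 8.2), and the sample size does not depend on this point. Practice may also already be right: the flowchart cited in section 8.3 is not reproduced, and the data-capture form mentioned in 12.1 is not among the documents. All of this stands, and no bias in the group comparison is claimed.

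**Conclusion.** The concern holds, as a minor inconsistency in the definition of the primary endpoint. A total of at least 3 is necessary but not sufficient for the criteria in 1.5.1: 9 of the 17 patterns that reach the total fail a listed criterion, three of them because the airway score is 0. The literal wording of section 2 can bring the time-stamp forward and can never delay it. The same form of words is exact for the recovery room and fails only for the primary endpoint.

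That the rules differ rests only on the scale and thresholds printed in the protocol. That the domain rule is the intended one is an inference from 1.5.1, 8.1.1 and the Summary. The share of children affected, and the size and direction of any effect on the difference between groups, cannot be determined from the documents.

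**What to change.** - **Sections 2 and 10.1:** replace the bracketed total with: first time at which all three Steward domains (Consciousness, Airway, Movement) score at least 1, as listed in 1.5.1.
- **Section 8.1.1:** refer to that same definition.
- **Section 1.5.1:** delete the sentence on the total, or reword it to say that the criteria imply a total of at least 3 but are not implied by it.
- **Data capture:** record the three domain scores at the time-stamp, if this is not already done. A total cannot be formed without scoring the domains, so this adds at most three fields.

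The cost is wording plus, at most, those three fields. Sample size and choice of test are unchanged. Recorded times can be no shorter than under the total-score rule.

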4.4 Sample size calculation

There are no previous studies about DSA and the speed of recovery after general anaesthesia.

Based on clinical experience we expect a medium to large effect size so we performed a power analysis using G* power software package with an effect size d of 0.6. The Wilcoxon-Mann-Whitney test was used as statistical test. A sample size of 51 patients per study group is required to achieve a power of 0.9 with an alpha error probability of 0.05.¹⁶ In order to compensate for possible dropouts due to protocol violation or data registration failure a total of 56 patients will have to be included in either group (+10%).

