8.2 Randomisation, blinding and treatment allocation

Patients will be allocated to either the intervention group or the control group by a computer-generated block randomisation. A paediatric anaesthetist who is not otherwise involved in this trial will perform the randomisation procedure, including the preparation of sealed envelopes with the randomisation codes per patient and the randomisation schedule.

The investigator who determines the hypnotic state of the patient after discontinuation of delivery of anaesthetic drugs is not present at the operating theatre during the surgical procedure. He enters the theatre at the moment of discontinuation of drug delivery, which equals the start of the emergence period. That enables us to blind the investigator as to the study-group assignment of the patient.

The member of the research team that provides general anaesthesia cannot be blinded with respect to group allocation. In patients allocated to the control group the screen of the Narcotrend monitor is obscured.

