10.2 Secondary study parameter(s)

Intergroup comparison of total time from discontinuation of hypnotic drug delivery until discharge from the post-anaesthesia care unit will be performed by means of an unpaired t-test or a Mann-Whitney-U-test.

Intergroup comparison of the incidence of postoperative delirium will be performed by means of an chi square test.

Posthoc intergroup comparison of hypnotic depth as measured by DSA is performed as follows: DSA patterns recorded during the procedure are categorised and assigned to three conditions of the specific DSA pattern for GA; appropriate DoH (presence of high power delta and alpha oscillations on the power spectrum), to deep DoH (presence of high power delta, alpha and theta oscillations on the power spectrum), to light DoH (presence of high power delta with the absence of high power alpha oscillations and the presence of high power beta oscillations). Intergroup comparison will be performed by a means of a chi-square test.

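### An unspecified normality test chooses the primary analysis after the data are seen, with no effect estimate or CI named and age unused; one rank-based analysis adjusted for age would settle all three

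*Combined protocol and SAP*

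**What the plan says.** Section 10.1 compares the time from the end of anaesthetic delivery to a Steward score of at least 3. It states "Therefore datasets will first be tested for normality by means of the Shapiro-Wilk normality test" and then "As appropriate, either a Mann-Whitney-U-test or a t-test will be performed". It gives no level for the normality test. It does not say whether the test is run in each arm or on the pooled data, and it has no rule for one arm passing while the other fails.

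Section 10.2 leaves the same choice open for time to recovery-room discharge ("performed by means of an unpaired t-test or a Mann-Whitney-U-test"). Section 10.3 repeats the gate with the same gaps ("All datasets will be tested for normality by means of the Shapiro-Wilk normality test"). Beyond that it offers only description: "Descriptive statistics will be applied to demographic variables, continuous variables such as discharge times". No part of section 10 names a between-group estimate, a confidence interval, a covariate or the sidedness of the test.

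Section 4.4, by contrast, commits to one test for sizing: "The Wilcoxon-Mann-Whitney test was used as statistical test", with d = 0.6, power 0.9, alpha 0.05 and 51 per group.

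On age, section 4.2 admits "Age > 6 months and < 12 years". Section 8.2 allocates patients to "either the intervention group or the control group by a computer-generated block randomisation" and mentions no stratification. Section 1.4 says MAC falls as age rises, and section 1.2 says the EEG effects of anaesthetics depend on age. The Summary and section 3 give the control arm one end-tidal target for all ages.

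**The concern.** A t-test is about a difference in means and a Mann-Whitney test is about ranks. Under section 10.1 the data decide which of these the trial reports, through a preliminary test whose level and input the analyst must choose. The test used for sizing may then not be the test used for the result. Whichever test is run, the plan commits only to a p-value, yet a reader needs to know how much faster emergence is and how precisely that is known.

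Age is a separate missed opportunity. It is a baseline value the trial already holds, the age range is wide, and the protocol gives reasons to think age could be related to emergence. The plan makes no use of it.

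**Working it through.** **1. The plan's own figure.** For a normal parent, Wilcoxon-Mann-Whitney power is close to that of a t-test with n multiplied by 3/π = 0.955.

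- Effective n: 51 × 0.955 = 48.7 per arm.
- Noncentrality: 0.6 × √(48.7/2) = 2.96.
- Power at alpha 0.05: 0.902 one-sided, 0.834 two-sided.
- n per arm for power 0.90: 51 one-sided, 63 two-sided.

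The stated 51 is thus reproduced as a one-sided calculation. The documents do not state sidedness. The figures below are two-sided, so their baseline is about 0.83 and not 0.90.

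**2. What the gate does.** Inputs from section 4.4 are 51 per arm and d = 0.6. The documents give no distribution, so lognormal times are an assumption, with log SD varied from 0.1 (little skew) to 0.5 (marked skew) and d applied on the log scale. There are 4,000 simulated trials per column. The six readings are per-arm or pooled, each at level 0.01, 0.05 or 0.10.

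| Log SD | 0.1 | 0.2 | 0.3 | 0.4 | 0.5 |
|---|---|---|---|---|---|
| t-test chosen, per-arm gate at 0.05 | 79% | 48% | 18% | 4% | 0.5% |
| t-test chosen, pooled gate at 0.05 | 80% | 41% | 10% | 1% | 0.1% |
| Per-arm and pooled gates choose different tests | 17% | 23% | 13% | 3% | 0.4% |
| ...and significance at 0.05 changes | 0.85% | 0.85% | 0.53% | 0.18% | 0.03% |
| Six readings do not all choose the same test | 38% | 56% | 39% | 14% | 4% |
| ...and significance is not the same under all six | 2.0% | 3.0% | 1.8% | 0.7% | 0.2% |
| Power, gated procedure | 0.837 | 0.840 | 0.840 | 0.824 | 0.822 |
| Power, Mann-Whitney alone | 0.824 | 0.831 | 0.836 | 0.823 | 0.821 |
| Type I error, gated procedure | 0.046 | 0.051 | 0.057 | 0.058 | 0.051 |

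The Monte Carlo standard error of the type I error is about 0.0035. A separate run of 8,000 trials per scenario put it at 0.045 to 0.054. In that run, at log SD 0.4, the gated procedure and the ungated Mann-Whitney test both gave 0.054, so the gate adds nothing there. Always taking the most favourable of the six readings adds at most about 0.4 points.

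**3. What age could add.** Quade's test works as follows:

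- Rank all emergence times and all ages over both arms.
- Regress the time ranks on the age ranks.
- Compare the residuals between groups.

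The documents give no correlation r between age and emergence time, so r is an assumption, shown from zero upwards.

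| Where age acts | r | Mann-Whitney | Age-adjusted rank test | Gain (points) |
|---|---|---|---|---|
| Nowhere | 0 | 0.836 | 0.836 | 0.0 |
| Both arms | 0.3 | 0.833 | 0.862 | 2.9 |
| Both arms | 0.5 | 0.821 | 0.908 | 8.7 |
| Control arm only | 0.3 | 0.832 | 0.834 | 0.2 |
| Control arm only | 0.5 | 0.828 | 0.850 | 2.2 |

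Type I error is 0.050 to 0.054.

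**4. Why not a log-time model.** A regression of log time is the obvious single-model alternative, but it is fragile to very short times. Assume whole-minute recording and 2% of times recorded as zero and set to half a minute. Two-sided power of the log-time test against Mann-Whitney is then 0.50 against 0.79 at log SD 0.3, and 0.70 against 0.81 at log SD 0.5. The documents do not say whether zeros will occur or what the recording unit is, so this loss is conditional. A rank test treats zeros as ties and does not depend on such a rule.

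**The case against.** The strongest reply is that the consequence is small. Type I error is near nominal, power matches Mann-Whitney, and even across six readings of the gate significance changes in at most 3.0% of trials. If emergence times are clearly skewed, the outcome is also nearly known in advance: with a per-arm gate at 0.05, Mann-Whitney is chosen in about 96% of trials at log SD 0.4 and 99.5% at 0.5. All of this stands. It confines the uncertainty over the test to low skew, but it does not supply the missing estimate and interval, which are absent at every degree of skew.

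A second reply is that age adjustment is optional. Sections 1.2 and 1.4 concern EEG patterns and MAC, not emergence time. With one end-tidal target for all control patients and individual titration in the other arm, an age effect mainly in the control arm is at least as plausible as one in both, and there the gain is slight. This also stands. The larger gains need a correlation that the documents do not give.

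Two stronger readings might be inferred, and neither is supported. One is that pre-testing for normality invalidates the primary p-value; the simulations show no material inflation. The other is that leaving age out, without stratification, biases the comparison; under randomisation it does not, and the only issue is precision.

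**Conclusion.** The point holds as a fault of specification and missed precision, not of error control. Section 10.1 leaves the primary quantity to be settled after the data are seen, departs from the single test named in section 4.4, and comes with no effect estimate or interval. On its own the gate is little more than missing detail. What makes the change worthwhile is that one fixed analysis can remove the gate, keep the method used for sizing, and use age at no visible cost in power (0.836 against 0.836 at r = 0).

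The potential gain is 0 to about 9 points if age acts in both arms and 0 to about 2 points if it acts in the control arm only, for r up to 0.5. These figures rest on assumed lognormal times, d = 0.6 on the log scale, 51 analysed per arm, a two-sided 0.05 test and an assumed correlation. The plan should make the change, but a trial run as written would still give a valid test.

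**What to change.** In section 10.1, before any outcome is examined by group:

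- Delete the Shapiro-Wilk gate.
- Name one primary analysis: rank analysis of covariance (Quade's test) of emergence time by study group, with continuous age as the covariate.
- Report the Hodges-Lehmann difference in emergence time with its 95% CI as the effect.
- Make the unadjusted Mann-Whitney test the single sensitivity analysis.
- State whether the primary test is one- or two-sided, consistently with section 4.4.

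Do not make a regression of log time the primary analysis, for the reason in step 4 of the working.

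The cost is wording only, since age is already collected for eligibility. There are two downsides to accept. The adjustment assumes a monotone relation between age and emergence time. The Hodges-Lehmann estimate and its interval are not themselves age-adjusted, so near the significance boundary they may not agree exactly with the adjusted p-value; the plan should say so in advance.
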